6.2.1.2 Primary efficacy variable: supportive analysis

The primary analysis of the primary efficacy variable will be repeated in the PPS as a supportive analysis. For the PPS analysis, the censoring rules for the primary analysis

specified in Section 6.2.1.1 will be further restricted to events occurring up to 30 days after last study drug intake.

Accordingly, subjects with censoring or event date more than 30 days after last study drug intake in the primary analysis will be censored at the date of last study drug intake +30 days.

The following supportive analyses of the primary efficacy variable will be performed in the FAS and PPS unless specified otherwise.

The originally planned presentation of absolute and relative frequency of subjects with an event of the primary composite endpoint will be superseded by the Kaplan-Meier estimates described below.

Kaplan-Meier estimates of the time to the first event of the primary composite endpoint (including 95% confidence interval, calculated based on a normal approximation and using the Greenwood formula for the standard deviation [4]), overall survival rates at appropriate time points and Kaplan-Meier curves will be presented for each treatment group. In this context, “survival” means no event of the respective primary efficacy endpoint. These analyses will be presented in total and for each level of the stratification factors.

For the primary composite endpoint and the individual events, the incidence rate per 100 patient-years will be presented by treatment group, which is defined as the number of subjects with an event divided by the time a patient is at risk for the respective event, i.e. either the time from randomization until the first event or the censoring time, multiplied by 365.25*100. Kaplan-Meier plots, logrank tests and Cox proportional hazards regression for the time to first event of the individual components will also be provided as part of exploratory efficacy (see section 6.2.3).

An ‘*on-treatment*’ analysis will also be performed, repeating the inferential statistics (stratified logrank test and stratified Cox regression model) on the FAS. For the on-treatment analysis, as described for the PPS analysis above, the censoring rules for the primary analysis will be adapted by further restricting to events occurring up to 30 days after last study drug intake.

The logrank test as well as the Cox regression model will also be performed without including stratification factors. The plausibility of the proportional hazards assumption will be assessed by visually examining the plot of the log of the negative log of Kaplan-Meier estimates of the survival function versus log time for evidence of non-parallelism, and by including a treatment by log-transformed time interaction into the Cox model. For the latter, the SAS code is adapted as follows:

```
PROC PHREG DATA = <dataset>;  
  MODEL ttevalue * ttecnsr(1) = trtgrpn trtotime / RL  
  TIES=EFRON ALPHA=0.05;  
  STRATA {stratum};  
  trtotime = trtgrpn*log(ttevalue);  
RUN;
```

The significance of the interaction will be tested at the 5% type I error level. If the interaction is significant and there is strong evidence of non-proportionality from the plots, time-dependent hazard ratios will be estimated with the model that includes the interaction term.

The censoring mechanism of subjects without an event of the primary composite endpoint at the time of analysis is assumed to be non-informative for the primary efficacy analysis. This also implies that the primary analysis is valid under a missing at random (MAR) assumption. Sensitivity analyses will be performed, assessing the impact of a potential informative censoring of subjects lost to follow-up or with withdrawn consent. Non-renal deaths will be treated as censored observations as in the primary analysis.

A summary of the amount of missing data by treatment arm will be given, including number of subjects who have incomplete follow-up on the respective endpoint.

Robustness with respect to missing data will be investigated with a tipping point analysis on the FAS (based on the ITT approach). The analysis will:

- Estimate the hazard at time of loss to follow-up, using a Weibull survival model fitted to the population of subjects who prematurely discontinued study treatment and adjusted for treatment group and stratification factors.
- Inflate the hazard only in the finerenone group by a known factor; assumes non-informative censoring in the control group.
- Impute events to the end of the study 1000 times, calculate the hazard ratios with the stratified Cox model specified in section 6.2.1.1 and combine them using standard multiple imputation combining rules.
- Increase the inflation factor until upper limit of two-sided confidence interval for the hazard ratio crosses 1.0; this will be the “tipping point”. The actual confidence level of the above mentioned confidence interval will depend on whether the study is stopped for overwhelming efficacy at the interim analysis or not, and on the p-value of the primary analysis of the key secondary endpoint. The confidence intervals will be as follows:
 - At the interim analysis: Use two-sided 99.73% confidence interval
 - At the final analysis:
 - p-value of primary analysis of key secondary endpoint < 0.01576184 :
Use two-sided 95.032612% confidence interval
 - p-value of primary analysis of key secondary endpoint ≥ 0.01576184 :
Use two-sided 96.717305% confidence interval

The tipping point will show how much higher the event risk after drop-out would need to be in the finerenone group so that statistical significance is lost. Since there is no particular reason to assume that the event rate should be higher, a large tipping point will indicate robustness of the study results. Technical details of the model are provided in section 9.1.

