6.4 Withdrawal of subjects from study

6.4.1 Withdrawal

6.4.1.1 Discontinuation of study drug - *amended*

This section was changed in Amendment 3, see Section 15.1.2.6.

After randomization, discontinuation of **study drug** (for any reason) does not constitute the subject's withdrawal from the **study** (see also Section 6.4.1.2).

Study drug *must* be permanently discontinued if any of the following occurs:

- Pregnancy of the study subject (see also Section 9.6.2)
- The investigator is of the opinion that continuation of treatment with study drug is harmful to the subject's well-being
- The randomization code is broken by the investigator, or other responsible person, when knowledge of the subject's treatment is required
- Any investigational drug other than the study drug is used.

Study drug *may* be permanently discontinued if any of the following occurs:

- Any suspected drug-related AE or SAE
- If any exclusion criterion applies during treatment
- If a significant violation of the protocol occurs, as defined by the sponsor and the coordinating investigator.

In general, subjects who permanently discontinue study drug are expected to continue in the follow-up period and to attend all protocol-specified study visits, and should be encouraged to perform all assessments described in the visit schedule (see Section 9.2).

If a subject no longer on study drug is unable to attend the clinic for a study visit, a telephone consultation may be performed to determine if relevant health events /endpoints (e.g. development of CV or renal complications) have occurred. Ideally, a face-to-face visit should be performed at least once a year. Expected frequency of telephone contacts should be in line with the standard visit schedule, and therefore performed every 4 months. Ad hoc additional telephone contacts may also be requested (e.g. prior to the interim analysis) and made to the subject themselves or to other contact as provided by the patient, e.g. a next of kin, primary physician (or local equivalent).

Note that study drug may be temporarily discontinued (i.e. interrupted), as described in Section 7.4.

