10.4 Determination of sample size - amended

This section was changed in Amendment 3, see Section 15.1.2.41.

This is an event-driven study. A total of 1068 primary efficacy endpoint events will have a minimum 90% power to demonstrate superiority of finerenone to placebo using a logrank test at a two-sided significance level of 3.3333%, assuming a 20% relative risk reduction, i.e. a true hazard ratio of 0.80 (the hazard ratio that will be observed in the study will be different, i.e. closer to 1 due to treatment discontinuations). The study will stop when at least 1068 primary efficacy endpoints accrue across both treatment arms.

With an assumed treatment duration of 44 months (duration of recruitment period: 33 months, equal recruitment pattern during the accrual period, maximum treatment period of the last subject recruited: 11 months), the planned total number of subjects to be randomized is estimated to be 4690 subjects, assuming an annual placebo event rate of 12%, a common annual lost-to-follow-up rate of 0.7% in both treatment groups, an annual finerenone discontinuation rate of 5% and assuming that placebo discontinuation will not change the hazard. 4800 subjects are planned to be randomized taking a certain ramp-up during recruitment into account. Assuming a screening failure rate of 50%, 9600 subjects are planned to be screened.

Due to the minimal effect of the interim analysis on the overall power of the study, an adjustment of sample size would be negligible.

The assumption of the annual placebo event rate of 12% is based on a recent analysis of the results from the IDNT and RENAAL trials using alternative endpoints defined by smaller declines in eGFR, similar to those proposed in Study 16244. Event rates were obtained from the respective studies in the arms where treatment would more closely resemble that in the placebo population of study 16244 who will be on standard of care treatment for DKD. Annual event rates for the composite renal endpoint range from 11-16% for these studies. The planned population of study 16244 will have some differences compared to IDNT and RENAAL, with a likely lower median UACR value but comparable mean eGFR. The comorbidity of diabetic retinopathy in subjects with high albuminuria may predict a higher

rate of renal events. Consequently, the assumed annual placebo event rate of 12% is assumed to be appropriate for this Phase III setting (10, 11).

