6.2 Efficacy

6.2.1 Analysis of primary efficacy variable

6.2.1.1 Primary efficacy variable: primary analysis

The primary efficacy variable is the time to first occurrence of the composite endpoint of onset of kidney failure, a sustained decrease of eGFR $\geq 40\%$ from baseline over at least 4 weeks, or renal death. All events classifying for the primary endpoint have to be adjudicated positively by an independent adjudication committee.

The primary analysis of the primary efficacy variable will be performed in the FAS.

Events for inclusion in the primary analysis will be counted from the day of randomization (planned at Visit 1) onwards until the EOS visit following the study termination decision, or until the date of EOS notification + 4 weeks, if the EOS visit has not been performed. In the event of premature discontinuation from the study with no subsequent follow-up information, renal events will be counted up to the day of the last visit when complete information on all components of the composite renal endpoint is available with an additional rule for events occurring after this visit. To account for events of kidney failure or renal death after the last eGFR is recorded at a clinic visit, such events will be included in the efficacy analysis if they occur in the period up to one day before the next planned clinic visit. This period would be a maximum of 5 months, given the next scheduled clinic visit should take place 4 months later, plus a time window for late attendance of one month. In addition, should the subject have a non-renal death in this period then the date of death will be used as the censoring date.

Randomized subjects without an event of the renal composite endpoint at the time of analysis will be censored at the date of their last visit when complete information on all components of the composite renal endpoint is available, up to and including the EOS visit (should this visit satisfy this rule), or date of non-renal death using a time window of 5 months as above if a subsequent clinic visit had been planned. Subjects without any information about the primary composite endpoint after baseline will be censored at Day 1.

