For subjects with consent withdrawn or who are lost to follow-up and who did not experience a primary efficacy endpoint, random variables will be simulated using the conditional time to event distribution after the last contact date given that no event was observed before. If this randomly generated variable has a value less than the elapsed time between the last contact date and the global cut-off date, i.e. the date when all subjects should have performed their EOS visit (notification of study termination + 4 weeks), the subject will be counted as having observed an event at the last contact date plus the random variable. Otherwise, the subject is re-adjusted to be censored at the global cut-off date.

These imputed events will be added to the observed events in the study and the primary efficacy variable will be re-analyzed. This process will be repeated 1000 times. For the final analysis, the hazard ratio with 95.032612% or 96.717305% confidence intervals (the actual confidence level will depend on the p-value of the primary analysis of the key secondary endpoint and is adjusted for the interim analysis, for further details see Section 6.2.1.2) will be estimated for each imputed data set and then combined using standard multiple imputation combining rules.

Details:

When the survival time T follows a Weibull distribution with survival function S_2 , then the conditional distribution function of time T after the last contact date/censoring date (LC) is given for $x \geq 0$ by:

$$\begin{aligned} y &= \Pr(T \leq x + LC | T > LC) = 1 - \Pr(T > x + LC | T > LC) \\ &= 1 - \frac{\Pr(T > x + LC)}{\Pr(T > LC)} = 1 - \frac{S_2(x + LC)}{S_2(LC)} \end{aligned}$$

With the estimated shape parameter β and the scale parameter λ from the underlying Weibull model, this results in:

$$\begin{aligned} y &= 1 - \exp\left(-\left(\frac{x + LC}{\lambda}\right)^\beta\right) / \exp\left(-\left(\frac{LC}{\lambda}\right)^\beta\right) \\ &\equiv \log(1 - y) = -\left(\frac{x + LC}{\lambda}\right)^\beta + \left(\frac{LC}{\lambda}\right)^\beta \\ &\equiv x = \lambda \times \left(\left(\frac{LC}{\lambda}\right)^\beta - \log(1 - y)\right)^{1/\beta} - LC \end{aligned}$$

If y is replaced with a random variable with uniform distribution between 0 and 1, the random variable x can be generated using the inverse transformation technique from

$$\lambda \times \left(\left(\frac{LC}{\lambda}\right)^\beta - \log(1 - \text{rand}('uniform'))\right)^{1/\beta} - LC.$$

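### The tipping-point analysis is specified for withdrawn or lost subjects from last contact, so renal follow-up missing in subjects followed only by telephone is not clearly imputed

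*SAP*

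**What the plan says.** **Follow-up after stopping drug.** Stopping study drug is not withdrawal from the study (Protocol 6.4.1.1, 11.4). "If a subject no longer on study drug is unable to attend the clinic for a study visit, a telephone consultation may be performed", on the 4-monthly visit schedule, and endpoint information is sought until the study ends (Protocol 9.1, 11.4). A face-to-face visit at least yearly is described as the ideal.

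**Renal censoring.** Under SAP 6.2.1.1, event-free subjects "will be censored at the date of their last visit when complete information on all components of the composite renal endpoint is available". For kidney failure or renal death after the last recorded eGFR, "such events will be included in the efficacy analysis if they occur in the period up to one day before the next planned clinic visit", at most 5 months. That rule follows a sentence about subjects who leave the study with no further information.

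**Sensitivity analysis.** SAP 6.2.1.2 describes analyses "assessing the impact of a potential informative censoring of subjects lost to follow-up or with withdrawn consent" and takes a large tipping point as a sign of robust results. SAP 9.1 (Appendix A) says: "For subjects with consent withdrawn or who are lost to follow-up and who did not experience a primary efficacy endpoint, random variables will be simulated", and names the last contact date as the starting point.

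**Text pointing the other way.** The opening paragraph of Appendix A speaks of imputing for living patients censored before the global cut-off date. The derivation later in Appendix A labels LC as the last contact date or censoring date, as if the two were the same. Protocol 10.3.3.2 describes the sensitivity analyses for subjects without a primary event generally.

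**The concern.** A telephone call gives no creatinine. It can report dialysis, transplant or death, but not a sustained eGFR fall of 40% or an eGFR below 15. A telephone-only subject is therefore censored at the last complete clinic visit although contact continues, perhaps to study end. That subject is neither withdrawn nor lost in the usual sense, and the last contact date may be close to the cut-off. On the plain wording of SAP 6.2.1.2 and the simulation step in Appendix A, the subject is not imputed. If imputed from last contact, almost no time remains to impute.

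This follow-up pattern arises after drug is stopped, so it may be related to prognosis and may differ by arm. A tipping point that omits it would be reported as evidence of robustness to missing renal data while one plausible source of informative censoring went untested.

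**Working it through.** **1. The plan's own figures.** Protocol 10.4: "A total of 1068 primary efficacy endpoint events will have a minimum 90% power" at a "two-sided significance level of 3.3333"%, "assuming a 20% relative risk reduction, i.e. a true hazard ratio of 0.80".

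- The simple formula 4(z₁₋α/₂ + z₁₋β)² / (ln HR)² gives 4(2.128 + 1.282)² / (ln 0.80)² = 934 events, so it does not explain 1068.
- A Lakatos-type log-rank calculation does. It uses 33 months of uniform accrual plus 11 months, a 12% annual placebo rate, 0.7% annual loss, and 5% annual finerenone discontinuation with return to the placebo hazard. It gives 1070.6 events, 89.9% power at 1068, and N = 4691 for 1068 events (stated: 4690).

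**2. Loss against discontinuation on those inputs (N = 4690).**

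- Lost to follow-up before an event: about 33 finerenone and 32 placebo, 65 in total.
- Finerenone subjects stopping drug before an event: about 226. No placebo discontinuation rate is given.
- If a share s of the 226 become telephone-only, their fraction of that arm's incomplete renal follow-up is 226s / (226s + 33): 41% at s = 10%, 58% at 20%, 77% at 50%. It passes one half at s = 33/226, about 14.5%. Consent withdrawals beyond the 0.7% would lower these fractions.

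**3. Size at the enlarged sample.** SAP section 3 gives approximately 5800 subjects, adopted because events were slower than assumed. Assumptions: follow-up u uniform from 11 to 44 months (mean 27.5); discontinuation d = 5% per year in both arms; loss l = 0.7% per year; a common event rate h chosen so that 5800 subjects yield about 1068 events.

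- Total events: 5800 × mean over u of h/(h+l) × [1 − exp(−(h+l)u)]. This gives 1070 at h = 0.091 per year as a hazard, or at 8.7% as an annual probability, so about 9% per year.
- Event-free discontinuers: 5800 × mean over u of d/(h+d+l) × [1 − exp(−(h+d+l)u)]. Result: 554 (hazards) or 567 (annual probabilities), with about 1.35 years left on average before study end.
- Events expected among them after stopping: 5800 × mean over u of ∫₀ᵘ d·exp(−(h+d+l)t) × h/(h+l) × [1 − exp(−(h+l)(u−t))] dt. Result: about 62 or 64.

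| Telephone-only share (assumed) | Event-free subjects | Events | % of 1068 |
|---|---|---|---|
| 20% | 111-113 | 12.4-12.7 | 1.2 |
| 50% | 277-284 | 31-32 | 2.9-3.0 |

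This takes the last complete renal visit as the day drug is stopped, assumes no later clinic visit, and applies the common event rate after stopping. Clinic attendance after stopping reduces the figures; a higher event rate after stopping would raise them.

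**4. The Appendix A wordings side by side.**

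| Item | Narrow text | Wider text |
|---|---|---|
| Who is imputed | Withdrawn or lost subjects (6.2.1.2; simulation step in 9.1) | Living patients censored before the cut-off (opening of 9.1) |
| Start of imputation | Last contact date (simulation step) | Time of censoring (opening of 9.1); contact or censoring date (derivation) |

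For a subject who is truly lost, the two start dates are close. For a telephone-only subject they can differ by as long as renal follow-up is missing.

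**The case against.** The strongest reply is that Appendix A already contains the right rule. Its opening paragraph covers any living patient censored before the cut-off and bases imputation on the hazard at censoring, and LC can be read as the censoring date. Lost to follow-up is not defined for the renal endpoint either. This stands to the extent that exclusion is not certain. It does not remove the problem: the opening paragraph derives its hazards for withdrawn or lost subjects, and the simulation step names those subjects and repeatedly uses last contact. Programmers could implement either rule.

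The gap may also be small. Off-drug subjects are expected to attend all visits, the yearly visit includes central laboratory work, and SAP section 3 requires that they be asked to attend the EOS visit. Any such visit with complete renal information moves the censoring date forward. That stands, and it is why the sizes above are conditional.

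SAP 6.2.1.2 also requires a summary by arm of subjects with incomplete follow-up on the endpoint. That would show the group, but it does not test its effect. Protocol 11.4 links the sensitivity analyses to consent withdrawals, so the protocol is not uniform; the SAP is still narrower than Protocol 10.3.3.2.

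A reader might infer that dialysis, transplant or renal death learned by telephone is thrown away after 5 months. The documents do not establish that. The general rule in SAP 6.2.1.1 counts events to the EOS visit, and the 5-month rule is introduced for subjects who left the study without further information. If it does not cover telephone subjects, their late hard events count while event-free telephone subjects are still censored at the last complete visit, so counting and censoring follow different rules. The text does not say which applies.

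**Conclusion.** The point holds as a conflict within the SAP and a gap in the reach of one sensitivity analysis. On its narrower wording, renal time missing because a subject is followed by telephone is outside the tipping-point analysis. The estimate of about 110-285 subjects and 12-32 events (1.2-3.0% of 1068) rests on the 5800 subjects in the SAP and on three assumptions: equal 5% discontinuation in both arms, about 9% events per year, and a 20-50% telephone share for which the documents give no figure.

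It might be inferred that the analysis misses most incomplete renal follow-up. On the plan's rates that would be so in the finerenone arm only above a telephone share of about 14.5%, and the documents do not give the share. The primary test, alpha and power are not affected. The change is worth making because it is cheap and because a large tipping point is to be read as robustness.

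**What to change.** - **SAP 6.2.1.2 and 9.1, imputation set:** every subject without a primary event or non-renal death whose renal censoring date precedes the EOS Visit (or the global cut-off if no EOS Visit took place), whatever the reason.
- **SAP 9.1, start date:** set LC to that renal censoring date throughout, replacing last contact date.
- **SAP 6.2.1.1:** state whether the 5-month rule applies to subjects still followed by telephone, so that event counting and censoring follow one rule.

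Cost: wording and slightly more programming on data already collected. The tipping point may look less favourable.
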